The participants who choose to consent and enroll in the study will then complete either the EEsAI (age 18 -60) or the PedsQL (age 6-17), both validated questionnaires that assess patient symptoms of EoE. Additionally, all study participants will have their initial Esophagogastroduodenoscopy (EGD) images evaluated via Endoscopic Reference Score (ERFS). This scoring system is a validated tool that has demonstrated moderate to good inter-observer variability. The PI for this protocol will be the physician who assigns a score to pre and post intervention images, in order to limit variations between graders. The 6-8 esophageal biopsies taken at initial EGD will be evaluated by pathology per routine protocol to provide primary diagnosis. Again to limit variation, there are two pathologists serving on this protocol as AIs that will be evaluating the specimens obtained during this research period. Each set of biopsies will then be evaluated by 1 of these 2 pathologists to record the number of eosinophils per high power field (HPF). Immunohistochemical staining on these biopsies for eotaxin-3 will be performed on the Ventana Ultra platform after stain optimization based on previously described protocols. Staining will be evaluated by 1 of 2 pathologists for intensity and percentage of cells staining (Allred scoring system). [name] will be performing research as a credentialed provider at WRNMMC Department of Pathology, although he is assigned to Joint Pathology Center.

The participants will be randomized into 2 groups: 1) omeprazole + swallowed fluticasone and 2) placebo + swallowed fluticasone. The placebo will replicate oral omeprazole. The study participants will be randomly assigned with concealment of allocation to one of the treatment groups, with each group having an equal number of participants (1:1 ratio).

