The EGDs will be performed according to standard of care. All pediatric patients undergoing EGD for evaluation of symptoms consistent with abdominal pain, dysphagia, vomiting, poor weight gain, etc., have the same endoscopic investigation and biopsy specimens obtained, regardless of what is seen. It is also standard of care for all adult subjects presenting with symptoms suggestive of EoE (dysphagia, food impaction) to undergo upper endoscopic evaluation with esophageal biopsies. Biopsy specimens will be sent to pathology for standard histological examination. A single pathologist will be assigned to review all of the slides and corroborate the findings on any abnormal results.

EGDs will be performed using Olympus GIF140 or 160 endoscopes. Each subject will undergo all the standard pre-operative evaluations including physicals done by the pediatric GI provider and anesthesia. The type of sedation or general anesthesia will be based on the assessment by the anesthesia team responsible for the subject during the EGD. All pediatric patients undergoing an EGD will have the same endoscopic evaluation regardless of the indication for the procedure. It is standard practice to obtain biopsies from the duodenum, stomach and esophagus during the initial EGD, however, follow up EGDs will include only esophageal biopsies.

Esophageal biopsy specimens sent to pathology will be examined and reviewed by the pathologists. For each subject, the specific number of eosinophils per high power field (HPF) will be collected. As previously mentioned, 1 of 2 participating pathologists will be assigned to review all the slides, and corroborate the specific number of eosinophils. This data is also documented as part of the subjects routine care, and thus the results will be maintained in the AHLTA electronic record system as well. As an additional outcome measure, tissue eotaxin-3 level, will be measured independently by 1 of 2 pathologists on all subjects.

Assessment	Visit/Follow up Interval				
	Day of identification	Within 2 weeks of consent	Week 4	Week 8	Week 8-10
Screening/Informed consent /Discuss plan	X				
Randomization	X				
Demographics	X				
Pt completes clinical questionnaire	X				
Begin treatment	X				
PI/AI reviews initial endoscopy findings		X			

Path stain esophageal tissue for eotaxin-3		X			
Phone follow up for compliance check			X		
EGD				X	
Pt completes clinical questionnaire				X	
Path stain for eotaxin-3 on repeat biopsies					X

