If the study involves collecting, storing, or banking human specimens, data, or documents (either by the Investigator or through an established repository) for FUTURE research, address. How the specimens /data will be used, where and how data/specimens will be stored (including shipping procedures, storage plan, etc.), whether and how consent will be obtained, procedures that will fulfill subjects' request as stated in the consent, whether subjects may withdraw their data/specimens from storage, whether and how subjects may be recontacted for future research and given the option to decline, whether there will be genetic testing on the specimens, who will have access to the data/specimens, and the linkage, the length of time that data/specimens will be stored and conditions under which data/specimens will be destroyed.

The specimens and data collected during the study period will be accessible to the researcher for future research studies if the subject provides consent. The data will be stored for a 10 year period in a de-identified file as described above. According to the standard operating procedure of the Pathology Department, the specimens will be kept with patient identifiers for a period of 10 years. The researcher will not extend this period or make any changes to the protocol. Subjects may withdraw their data and specimens at any time. The subjects will not be contacted for future research, unless requested. There will not be any genetic testing done on these specimens.

11.0

Statistical/Data Analysis Plan

11.1 Statistical Considerations:

List the statistical methods to be used to address the primary and secondary objectives, specific aims, and/or research hypotheses. Explain how missing data and outliers will be handled in the analysis. The analysis plan should be consistent with the study objectives. Include any sub-group analyses (e.g., gender or age group). Specify statistical methods and variables for each analysis. Describe how confounding variables will be controlled in the data analysis

See 11.4 below.

11.2 Sample Size:

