11.5 Please provide a justification for your sample size

The sample size was estimated for the primary outcome utilizing a two-sided likelihood ratio chi-square test of two independent proportions. The following parameters were used in this calculation: alpha of 0.05 and a power of 0.8. A response rate in the control group of fluticasone alone (reference proportion) was estimated to be 50% based on the study Konikoff et al (6). The estimated response rate for the treatment arms are based on clinical experience as was estimated to be in the range of 70% to 80%. This graph demonstrates that the sample size estimation may vary anywhere from 78 to 180 subjects. We plan to enroll approximately 100 patients.

11.6 Data Analysis Plan:

Outcome variables are listed in the following table. All continuous data will be evaluated for normality of the data using both univariate methods, visual inspection, and the Kolmogorov Smirnov test. Differences in continuous data that is normally distributed will be tested using parametric tests and for data that is not normally distributed a nonparametric test. Likert scale data will be transformed into numerical data and evaluated as continuous variables.

Outcome variables	Variable Type	Statistical Test
Primary Outcome Tissue esophageal eosinophils < 15/ hpf	Binary categorical	Two-sided likelihood ratio chi-square test of two independent proportions

Change in EEsAI	Likert scale - continuous	Normally distributed data: t-test Non-normally distributed data: Mann-Whitney U
Change in PedsQL	Likert scale - continuous	Normally distributed data: t-test Non-normally distributed data: Mann-Whitney U
Change in EREFS	Continuous	Normally distributed data: t-test Non-normally distributed data: Mann-Whitney U
Change in eosinophils per hpf	Continuous	Normally distributed data: t-test Non-normally distributed data: Mann-Whitney U
Change in tissue eotaxin level	Continuous	Normally distributed data: t-test Non-normally distributed data: Mann-Whitney U

Although all outcomes will be evaluated and reported using pooled data, a priori planned subgroup analysis will include a stratification of the analysis and results based on adult and pediatric subject groups.

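### Each subject's baseline and week-8 eotaxin-3 slides are stained in separate runs 6 to 10 weeks apart, so run-to-run variation enters the change score; staining them as a pair is a cheap gain in precision.

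*Combined protocol and SAP*

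**What the plan says.** The visit schedule at the end of section 10.1 (Study Procedures) has two staining rows. The first, "Path stain esophageal tissue for eotaxin-3", is marked in the column headed "Within 2 weeks of consent". The second, "Path stain for eotaxin-3 on repeat biopsies", is marked in the Week 8-10 column. Randomisation and the start of treatment are both marked on the day of identification.

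The text of section 10.1 says that the staining "will be performed on the Ventana Ultra platform after stain optimization based on previously described protocols". On reading, it says: "Staining will be evaluated by 1 of 2 pathologists for intensity and percentage of cells staining (Allred scoring system". Later in the same section the stain is ranked: "As an additional outcome measure, tissue eotaxin-3 level, will be measured independently by 1 of 2 pathologists on all subjects".

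The outcome table in section 11.6 (Data Analysis Plan) lists "Change in tissue eotaxin level" as a continuous variable, to be compared by t-test or Mann-Whitney U. It has no term for staining run or batch.

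On tissue, section 10.14 leaves storage to the Pathology Department's standard procedure, and section 10.15 adds that "the specimens will be kept with patient identifiers for a period of 10 years".

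No section asks for a subject's two samples to be stained together, for a control or reference slide in each run, or for baseline tissue to be re-stained.

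**The concern.** The endpoint is a within-subject difference in a semi-quantitative score, and one of its two components is stain intensity. Intensity can vary from run to run. If both of a subject's slides share a run, an additive run effect is subtracted out. If they never share one, two run effects go into the difference and neither cancels. Under this schedule they never share one.

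What is at stake is the precision of one non-primary outcome. That outcome does carry weight in the argument of the trial: section 9.3 rests the case for combination therapy on greater eotaxin-3 suppression with both drugs than with either alone, and this stain is the trial's in-vivo measure of it. A drift common to all subjects would also move the mean change seen within each arm, which readers are likely to take as the suppression achieved on that regimen.

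The early stain appears to serve no purpose in the plan. It may come up to two weeks after treatment has begun, so it cannot inform eligibility, allocation or the start of treatment, and no later decision refers to it.

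**Working it through.** **The plan's own figure.** There is none to reproduce. The sample-size text in sections 11.2 and 11.5 concerns the binary primary outcome only. The documents give no SD, effect size, power or run-to-run variance for eotaxin-3.

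**Step 1: gap between stainings.** Baseline falls in weeks 0 to 2 and the repeat in weeks 8 to 10. The shortest gap is 8 − 2 = 6 weeks and the longest 10 − 0 = 10 weeks. The windows do not overlap.

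**Step 2: effect on the change score.** Let the drift-free change score have SD 1, and let each run add an independent effect with SD r in those units.
- Separate runs: variance = 1 + r² + r² = 1 + 2r².
- Same run: the additive effect cancels, and the variance is 1.

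**Step 3: effect on power.** The inputs are 50 per arm (section 11.4) and two-sided alpha 0.05 with power 0.80, borrowed from the primary-outcome calculation as a reference point. The difference detectable without drift is (1.960 + 0.842) × √(2/50) = 2.802 × 0.2 = 0.56 SD. Power with separate runs is Φ(2.802/√(1 + 2r²) − 1.960). The n per arm that restores 80% is 50 × (1 + 2r²), rounded up. All values of r are assumptions.

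| r | Variance | SD | Power at 50 per arm | n per arm for 80% |
|---|---|---|---|---|
| 0 (same run) | 1.000 | 1.000 | 80% | 50 |
| 0.10 | 1.020 | 1.010 | 79% | 51 |
| 0.25 | 1.125 | 1.061 | 75% | 57 |
| 0.50 | 1.500 | 1.225 | 63% | 75 |

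**Step 4: bias between arms.** The same set-up was simulated with 4,000 replicates per setting, permuted blocks of 4 (block size assumed) and independent run effects per subject, with and without a common drift of 0.5 SD. With no true effect, the mean difference between arms was about 0.00 and the type I error 4.9% to 5.3%. With the 0.56 SD effect, power was 80% with paired staining, about 74% at r = 0.25 and 61% to 63% at r = 0.50, in line with the formula. A common drift shifts the mean change in each arm by its full size and cancels between arms.

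**The case against.** The strongest reply is that the loss may be negligible. Staining is on one named automated platform, optimised beforehand, and the score is coarse and partly a percentage of cells, so a small drift may not move it at all. If several subjects from both arms share a run, part of the run effect also cancels between arms, and the documents do not say how many share one. All of this stands. It means that the lower rows of the table may never apply. It does not remove the point, because optimisation before the study is not control of variation during it, and the remedy is nearly free.

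A reader might go further in four ways that the documents do not support.

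- **That the treatment comparison is biased.** Both arms follow the same schedule under concealed 1:1 randomisation, so drift is balanced in expectation, as Step 4 shows.
- **That the variance of the endpoint rises by 25% to 100%.** The ratio 1 + (b/w)², with between-run SD b and within-run SD w, gives 1.25, 1.56 and 2.00 for b/w of 0.5, 0.75 and 1.0. That is the measurement-error variance only, under assumed ratios. If measurement error is an assumed 20% of the total change-score variance, the total rises by 0.20 × 25%, 56% or 100%, that is 5%, 11% or 20%, and the standard error by about 2%, 5% or 10%.
- **That the pathologists are unblinded to visit.** The schedule fixes when tissue is stained, not how slides are presented. The abstract (section 9.1, under 2.3) calls the pathologists blinded. It does not say whether this covers visit, which needs clarifying but is not shown to be a failure.
- **That a planned within-arm result is invalid.** The aim and hypothesis in section 9.4 are between-arm, and section 11.6 lists no within-arm test. Only a descriptive within-arm change would be affected.

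**Conclusion.** The point holds as an inexpensive improvement in precision. As scheduled, every subject's two eotaxin-3 slides fall in different runs 6 to 10 weeks apart, and the planned analysis has nothing that removes run-to-run variation. The between-arm comparison is not biased, and the primary eosinophil outcome is not affected. The cost lies between almost nothing and a material loss: 80% power becomes about 79%, 75% or 63% at assumed run SDs of 0.10, 0.25 or 0.50 of the drift-free change-score SD. Those figures assume independent additive run effects for each subject and a normal approximation. The documents do not say which row is closest.

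The remedy depends on one inference. Section 10.15 speaks of specimens kept for 10 years. A reader might infer that archived blocks with usable tissue exist for every subject, but the documents do not say so, and it needs confirming with Pathology.

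**What to change.** In the section 10.1 schedule, move the baseline eotaxin-3 stain to the Week 8-10 column. Add to the staining text that, where stainable baseline tissue remains:

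- each subject's baseline and week-8 sections are cut and stained in the same run;
- slides are coded so that the reader knows neither visit nor arm;
- the same one of the two pathologists scores both slides of a subject, which the text does not now require.

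Baseline tissue from a subject without a week-8 biopsy is stained in a later run; it contributes no change score but can still describe the baseline.

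The cost is one schedule entry and a few sentences, with the same number of slides and reads. The downside is that baseline scores arrive about 8 weeks later, and no decision in the protocol uses them. Pairing removes only the additive part of a run effect.

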 2. EREFS
 3. Eosinophils per high power field on esophageal biopsies
 4. Tissue eotaxin-3 IHC score from esophageal biopsies

10.3 At any point in the study, will you request, use, or access data from a DoD Database or the Military Health System (MHS)?

Yes No

10.4 Review the definitions below and respond to the following two questions. If you are not sure of the answers, email [contact] for assistance.

The *Military Health System (MHS)* is defined as all DoD health plans and DoD health care providers that are organized under the management authority of, or in the case of covered individual providers, assigned to or employed by, the Defense Health Agency (DHA), the Army, the Navy, or the Air Force

***MHS workforce members* are employees, volunteers, trainees, and other persons whose conduct, in the performance of work for the MHS, is under the direct control of the MHS, whether or not they are paid by the MHS.**

***MHS business associates* are persons or entities that provide a service to the MHS and require protected health information (PHI) to provide the service.**

Are you an MHS workforce member?

Yes, I am an MHS workforce member
 No, I am not an MHS workforce member

Are you an MHS business associate?

Yes, I am an MHS business associate
 No, I am not an MHS business associate

10.5 Have you consulted with an MHS data expert to determine the data elements required for your study?

Consulting with a data expert often saves time later in the compliance process because the data expert can advise on the data available in the numerous MHS information systems, the quality of that data and the methods for encrypting and collapsing data. To schedule a consult with an MHS data expert, send an email to: ([contact])

Yes, then complete the questions below according to the data consult
 No, then complete the questions below according to the best of your knowledge

10.6 Indicate how you will request data from the MHS. Select all that apply.

- Talking with MHS health care providers or MHS health plans about specific research participants
- Obtaining MHS hard copy records specific to research participants
- Obtaining data from an MHS information system(s)

10.7 If you are obtaining data from an MHS information system(s), indicate whether you plan to receive a data extract or whether you plan to access an MHS information system directly to create a data set.

A data extract is when the MHS or a contractor provides the data set directly to the researcher. When receiving a data set through data extract, the researcher may indicate whether the data elements should

be provided as is, encrypted or collapsed. In contrast to a data extract, access to an information system means that the researcher may directly access an MHS information system and create a data set for the research study

- Data Extract
- Access

10.8 Do you intend to use only de-identified data from the MHS in your research study?

There are different two methods for de-identifying data pursuant to HIPAA:
 1) Safe Harbor Method: Removing all of the identifiers listed in Table 1 below, provided that the researcher does not have actual knowledge that the remaining data can be used alone or in combination with other information to identify the individual who is the subject of the information
 2) Statistical Method: An expert, with appropriate knowledge of and experience with generally accepted statistical and scientific principles and methods for rendering information not individually identifiable, determines that the data is not individually identifiable

- Yes
- No

10.9 Indicate the MHS information system(s) from which you will seek to obtain data

If you do not know which system(s) contains the data elements you need, refer to the Guide for DoD Researchers on Using MHS Data or request guidance from an MHS data expert at: **[contact].**

Below is a list of commonly used MHS systems. If the system from which you seek to obtain data is not listed below, list the name of the system in the "Other MHS Systems" category below

PHI Systems:

MHS Information System	Requesting Data
: AHLTA	: Yes
: CHCS	: Yes

PII-Only Systems:

MHS Information System	Requesting Data
No records have been added	

Information System	Requesting Data
No records have been added	

10.10 Do you intend to merge or otherwise associate the requested data with data from any sources outside of the MHS, including other DoD systems that are not part of the MHS?

- Yes, will merge data
- No, will not merge data

10.11 Indicate the data elements about research participants or relatives, employers, or household members of the research participants that you will request from MHS hard copies or from MHS information systems.

If you answered "yes" to question 10.9 above, also indicate non-MHS data elements about research participants or relatives, employers, or household members of the research participants that you will have access to in any form or medium.

Data Element(s)	MHS	Non-MHS Systems	MHS Hard Copies
-----------------	-----	-----------------	-----------------

1. Names			
2. Postal address with only town, city, state and zip code			
3. Postal address with all geographic subdivisions smaller than a state, including street address, city, county, precinct, zip code and their equivalent geocodes, except for the initial three digits of a zip code if, according to the current publicly available data from the Bureau of Census: 1) the geographic unit formed by combining all zip codes with the same three initial digits contains more than 20,000 people; and 2) the initial three digits of a zip code for all such geographic units containing 20,000 or fewer people is changed to 000			
4. Dates including all elements (except year) directly related to an individual, including birth date, admission date, discharge date, and date of death			
5. Ages over 89 and all elements of dates (including year) indicative of such age, unless you will only request a single category of "age 90 or older"			
6. Telephone numbers			
7. Fax numbers			
8. Electronic mail addresses			
9. Social Security numbers (SSNs)			
			

10. Medical record numbers			
11. Health plan beneficiary numbers			
12. Account numbers			
13. Certificate/license numbers			
14. Vehicle identifiers and serial numbers, including license plate numbers			
15. Device identifiers and serial numbers			
16. Web Universal Resource Locators (URLs)			
17. Internet Protocol (IP) address numbers			
18. Biometric identifiers, including finger and voice prints			
19. Full-face photographic images and any comparable images			
20. Any other unique identifying number, characteristic, or code (DEERs ID, EDIPN, Rank)			

If you are obtaining SSNs, provide a justification as to why and explain why a substitute cannot be used

10.12 Do you believe it is possible for the MHS data to become identifiable because of triangulation, a small cell size, or any unique data element(s)?

Triangulation means using different data elements that are not themselves identifiable but that when combined can be used to identify an individual. For example, triangulation would use rank and race together to determine the identity of an individual with a particular health condition.

Small cell size means that there is only a small number of eligible individuals that satisfy the category description. Guidance for acceptable cell size is available from the Centers for Medicare and Medicaid Services. For example, the rank category of four star generals with a particular diagnosis may be less than 30, so the rank category may need to be expanded to include lower ranks.

A unique data element includes any unique features that are not explicitly enumerated in the categories of data in rows 1 – 20 of the table above (in Section 10.10), but that could be used to identify an individual. Unique data elements include characteristics that are not themselves identifying, such as the rank of general or admiral, or a race or gender, but within the context of other information could be identifiable.

- Yes, I believe there is a reasonable possibility the MHS data will become identifiable
- No, I believe there is no reasonable possibility the MHS data will become identifiable

10.13 HIPAA Privacy Rule and Use of Protected Health Information in Research:

- N/A – will not use or disclose protected health information (PHI)
- HIPAA Authorization will be obtained
- Use of a limited data set where a data use agreement will be obtained
- Waiver/alteration of HIPAA Authorization is being requested

10.14 Managing Data (Data Management and/or Sharing Plan) and/or Human Biological Specimens for this Study:

Include in this section the plan for acquiring data (both electronic and hard copy), access during the study, data/specimen storage and length of time stored, shipment/transmission, and the plan for storage and final disposition at the conclusion of the study. Describe any data agreements in place for accessing data within and/or outside of your institution (e.g., Data Sharing Agreement, Data Use Agreement, Business Agreements, etc.)

The investigators will be responsible for accessing and reviewing medical record data for those patients who have been consented and chosen to participate in the study. Subjects will be referred for enrollment by their primary gastroenterologist. No PHI will be removed from the covered entity by the research team in the course of the review. All data will be stored and organized on a password protected spreadsheet file where the subject will be identified by an alpha-numeric code, rather than a name. Research records must be kept for a minimum of three years after the research is completed and the study closed with the IRB (32 CFR 219.115(b)), and for this study we will keep the master list for 5 years after the closure of the study, while all de-identified data will be kept for a period of 10 years after the closure of the study. Consent forms will be retained for 7 years following closure of study, and HIPAA Authorization will be retained for at least 6 years from the date of its creation or the date when it was last in effect, whichever is later (45 CFR 164.530(j) (1)).

Specimens obtained during endoscopy will be transferred, stored and kept based on the standard operating procedure in the Pathology Department. There will be no changes to this standard for the purposes of this study.

10.15 Managing Data (Data Management and/or Sharing Plan) and/or Human Biological Specimens for Future Research:

If the study involves collecting, storing, or banking human specimens, data, or documents (either by the Investigator or through an established repository) for FUTURE research, address. How the specimens /data will be used, where and how data/specimens will be stored (including shipping procedures, storage plan, etc.), whether and how consent will be obtained, procedures that will fulfill subjects' request as stated in the consent, whether subjects may withdraw their data/specimens from storage, whether and how subjects may be recontacted for future research and given the option to decline, whether there will be genetic testing on the specimens, who will have access to the data/specimens, and the linkage, the length of time that data/specimens will be stored and conditions under which data/specimens will be destroyed.

The specimens and data collected during the study period will be accessible to the researcher for future research studies if the subject provides consent. The data will be stored for a 10 year period in a de-identified file as described above. According to the standard operating procedure of the Pathology Department, the specimens will be kept with patient identifiers for a period of 10 years. The researcher will not extend this period or make any changes to the protocol. Subjects may withdraw their data and specimens at any time. The subjects will not be contacted for future research, unless requested. There will not be any genetic testing done on these specimens.

11.0

Statistical/Data Analysis Plan

11.1 Statistical Considerations:

List the statistical methods to be used to address the primary and secondary objectives, specific aims, and/or research hypotheses. Explain how missing data and outliers will be handled in the analysis. The analysis plan should be consistent with the study objectives. Include any sub-group analyses (e.g., gender or age group). Specify statistical methods and variables for each analysis. Describe how confounding variables will be controlled in the data analysis

See 11.4 below.

11.2 Sample Size:

The sample size was estimated for the primary outcome utilizing a two-sided likelihood ratio chi-square test of two independent proportions. The following parameters were used in this calculation: alpha of 0.05 and a power of 0.80. A response rate in the control group of fluticasone alone (reference proportion) was estimated to be 50% based on the study Konikoff et al.⁶ The estimated response rate for the treatment arms are based on clinical experience as was estimated to be in the range of 70% to 80%. This graph demonstrates that the sample size estimation may vary anywhere from 78 to 180 subjects. We plan to enroll approximately 100 patients.

11.3 Total number of subjects requested (including records and specimens):

100

11.4 If you are recruiting by study arm, please identify the arms of the study and how many subjects will be enrolled in each arm

50 subjects in each arm - one arm will be fluticasone and placebo, one arm will be fluticasone and omeprazole.

